4.10 Devices Used

The EnligHTN™ Renal Denervation System is designed to deliver radiofrequency (RF) energy to the renal nerves to achieve targeted denervation. The system consists of the EnligHTN™ RF Ablation Generator (generator), the EnligHTN™ Renal Artery Ablation Catheter (ablation catheter), and the EnligHTN™ Guiding Catheter (optional).

The manufacturer of the EnligHTN™ Renal Denervation System is St. Jude Medical, Cardiovascular Division, [name]

The following market approved St. Jude Medical devices to be initially used in this investigation are:

4.10.1 EnligHTN™ Renal Artery Ablation Catheter

The EnligHTN™ Renal Artery Ablation Catheter is a single use device that has an expandable electrode basket with four Platinum-Iridium (Pt-Ir) ablation electrodes. The electrodes deliver low-level radiofrequency energy to the renal arteries through a percutaneous vascular access site. The distal segment of the ablation catheter is deflectable to assist in proper basket positioning. The handle is used to actuate the expansion and relaxation of the basket, and to actuate the deflection of the ablation catheter at the distal end. The ablation electrodes and the tip are radiopaque to provide visualization under fluoroscopy.

4.10.2 EnligHTN™ RF Ablation Generator

The EnligHTN™ RF Ablation Generator delivers RF energy to the EnligHTN Renal Artery Ablation Catheter using a proprietary algorithm developed to produce a consistent, transmural ablation pattern during the renal denervation procedure.

4.10.3 EnligHTN™ Guiding Catheter (optional)

The EnligHTN™ Guiding Catheter system is comprised of two components: a guiding catheter and a dilator. The guiding catheter is constructed of three components: a polytetrafluoroethylene (PTFE) liner, a stainless steel braid, and a multi durometer polymer jacket. The proximal end of the catheter terminates in a hemostasis hub and a hemostasis valve. An extension tube and 3-way stopcock valve is attached to the sideport of the hemostasis hub. The distal end of the catheter terminates in a renal curve with a radiopaque marker embedded in the polymer jacket approximately 2 mm from the catheter tip. The dilator is a polymer tube with an inside diameter sized for guidewire clearance. The proximal end terminates in a snap fitting to mate with the guiding catheter hemostasis hub. The distal end is tapered to facilitate insertion through an introducer sheath.

Upon receiving CE mark, new generations of SJM devices for renal denervation may be used in this clinical investigation as they become available on the market.

4.11 Intended Use

The ablation catheter is indicated for use in renal denervation procedures for the treatment of resistant hypertension.

5 Procedures

Table 1: Data/CRF Collection

Activity \ Visit	Enrollment / Baseline	Procedure	Discharge <72 hrs	1M ±14d	6M ±30d	12M ±60d
PIS & PIC	X					
Inclusion/Exclusion	X					
Medical History	X					
Office Blood Pressure	X		X	X	X	X
Physical Assessment	X		X	X	X	X
Ambulatory Blood Pressure	X ^{1,2}			X ¹	X ¹	X ¹
NYHA Assessment	X			X	X	X
Serum creatinine	X				X	X
Estimated GFR	X				X	X
Urine albumin-to-creatinine ratio	X ¹				X ¹	X ¹
Medications	X		X	X	X	X
Renal Artery Anatomy Evaluation	X ¹	X			X ¹	
Pregnancy Test (urine / blood)	X ^{**}					
Renal Denervation Procedure		X				
Adverse Event Assessment	**	**	**	**	**	**
CIP Deviation	**	**	**	**	**	**
Withdrawal/ Termination		**	**	**	**	**
(**) As applicable (1) If done per clinical routine (2) Ambulatory Blood Pressure Recordings of the last 2 weeks can be used						

5.1 Enrollment/Baseline Visit

Prior to enrollment in the study, site personnel will evaluate potential candidates by reviewing the patient medical records against the inclusion and exclusion criteria. It is expected that the medical records will contain adequate and accurate information to determine if the patient meets these criteria.

If a patient meets all inclusion criteria and does not meet any of the exclusion criteria, the patient shall be eligible for the investigation.

If the patient agrees to participate, the study site personnel shall follow the informed consent process set forth in Section 6.6 and obtain the signature and date from the patient on the approved Patient Informed Consent (PIC) form (previously approved by Ethics Committee and the Sponsor). If the patient does not sign and date the Patient Informed Consent (PIC) form, they cannot participate in the investigation. No further CIP required activities are allowed.

A patient becomes a subject once he/she has been fully informed about the investigation, has agreed to participate, signed & dated the PIC form and therefore has been enrolled in the investigation.

NOTE: As soon as the subject signs the Patient Informed Consent form, adverse events need to be reported according to the guidelines mentioned in Section 6.7.8.

The EC should be notified appropriately about any CIP deviations with regards to obtaining informed consent.

If new information becomes available during the clinical study that can significantly affect a patient's future health and medical care, that information will be provided to the patient(s) in written form.

The following information will be collected at the baseline visit either from hospital records or through patient interaction documented in the hospital records. All baseline activities are performed after the patient is enrolled in the investigation. Ambulatory Blood Pressure (ABP) recordings performed as standard of care within 2 weeks before the baseline visit can be used. Other tests and required assessments performed as standard of care before the baseline visit can be used if done within 90 days prior to procedure.

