5.1.3 Office Blood Pressure

Office Blood Pressure measurements will be recorded as the average Blood Pressure of three measurements. If there is a change in medication after the office Blood Pressure assessment is completed an additional set of office Blood Pressure measurements is required to determine eligibility.

Measurements should be taken according to Standard Joint National Committee VII Guidelines / ESC and ESH Guidelines^{49, 50}.

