5.1.6 Blood/Urine Analysis

Blood and urine samples will be drawn and analyzed. The following results will be collected:

- Serum Creatinine
- eGFR
- Urine albumin-creatinine ratio (if available per standard of care)
- Pregnancy test (if applicable)

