5.2 Renal Denervation Procedure

The renal denervation procedure should always be done with the aid of fluoroscopy. After confirming subject renal artery anatomy and inclusion and exclusion criteria the site will prepare and perform the renal nerve ablation according to the EnligHTN™ Renal Denervation System Instructions for Use (IFU).

The investigator will select the appropriate basket size of the EnligHTN™ Renal Artery Ablation Catheter (small size for a renal artery diameter between 4mm and 6mm and large size for a renal artery diameter between 5.5mm and 8mm). The EnligHTN™ Renal Artery Ablation Catheter will be inserted with the tip of the catheter positioned proximal to the bifurcation of one of the main renal arteries and the corresponding images will be recorded. The basket on the EnligHTN™ Renal Artery Ablation Catheter will then be opened, while the impedance of each electrode on the basket will be monitored. To begin the ablation, the “START” button on the RF Generator will be pressed with the impedance, temperature and RF energy delivery monitored and recorded during the process. The investigator will decide the location(s) and number of ablation sites/lesions (4 to 8 ablation lesions are recommended) in the main renal artery. When the ablation procedure is completed in this main renal artery, the EnligHTN™ Renal Artery Ablation Catheter will be withdrawn from the artery with the basket fully closed. Images of the renal artery using a non-ionic contrast will be recorded. Any signs of renal artery irregularities (vasospasm, stenosis or dissection) will be checked.

The same renal artery ablation procedure will be repeated for the contra-lateral main renal artery. When the ablation procedure for the contra-lateral main renal artery is also completed, the EnligHTN™ Renal Artery Ablation Catheter will be withdrawn from the artery with the basket fully closed and the catheter will be visually inspected and flushed with heparinized saline. Finally, the sheath will be removed according to the institution’s standard of care.

Procedural data collected will include but is not limited to:

- EnligHTN™ Renal Denervation System device information
- Guiding catheter used – manufacturer
- Number of arteries ablated
- Number of ablations performed
- Device settings
- Procedure time
- Ablation time
- Fluoroscopy time
- Volume of contrast media

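### A pregnancy test up to 90 days old satisfies the plan's only scheduled test, and none is specified close to the fluoroscopic procedure (minor safety point)

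*Combined protocol and SAP*

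**What the plan says.** The default in section 5.1 is that "All baseline activities are performed after the patient is enrolled in the investigation". The same section then allows routine-care results to be used instead. For ambulatory blood pressure, "recordings performed as standard of care within 2 weeks before the baseline visit can be used". For everything else, "Other tests and required assessments performed as standard of care before the baseline visit can be used if done within 90 days prior to procedure".

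Section 5.1.6 lists the pregnancy test among the baseline blood and urine results, where applicable, and gives it no window. Table 1 marks it once, in the Enrollment/Baseline column; the Procedure column has no entry. Section 5.4.4 lists none at follow-up.

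On the procedure, section 5.2 says: "The renal denervation procedure should always be done with the aid of fluoroscopy". It also has contrast images of the renal artery recorded. On eligibility it says: "After confirming subject renal artery anatomy and inclusion and exclusion criteria the site will prepare and perform the renal nerve ablation".

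Section 4.5 excludes women who are pregnant or nursing, and women of childbearing potential without adequate contraception. It also says the procedure should take place within 30 days of enrolment.

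**The concern.** Pregnancy status can change within 90 days. A woman who conceives after an old negative test, for example through contraceptive failure, should be excluded under 4.5. If the site relies on the carried-over result, the only scheduled test will not show the pregnancy before she is exposed to fluoroscopy and contrast.

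Elsewhere the plan does refresh an eligibility result that may have gone out of date. Under 5.1.3, if medication changes after the office blood pressure assessment, "an additional set of office Blood Pressure measurements is required to determine eligibility". Pregnancy has no equivalent rule.

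What is at stake is a rare but avoidable exposure. The estimate of blood pressure reduction is not in question, and the carry-over rule does not contradict the exclusion in 4.5.

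**Working it through.** The plan gives no figure on this point to reproduce. The check is a reading of the rules, then day arithmetic, then a rough size.

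**1. Does the 90-day rule cover the pregnancy test?** Section 5.1 separates ambulatory blood pressure from all other tests. The pregnancy test is one of the others, and nothing in 5.1, 5.1.6 or Table 1 exempts it. The rule applies to a test already done as standard of care.

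**2. Does a later step require a newer test?** Section 5.2 requires the criteria to be confirmed but states neither a test nor a maximum age. Table 1 has no pregnancy test at the procedure visit. So the rules as written do not require one.

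**3. Oldest acceptable result at the procedure.**
- Carried over from routine care: 90 days.
- Done at the baseline visit, with the procedure within 30 days of enrolment: about 30 days. This is not a firm limit, because the 30-day interval is only a recommendation.
- For comparison, a carried-over ambulatory recording: 14 + 30 = 44 days, under the same condition.

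**4. Days removed by a tighter rule.**
- 7-day window before the procedure: 90 − 7 = 83 days.
- 14-day window: 90 − 14 = 76 days. 3-day window: 90 − 3 = 87 days.
- Testing at enrolment only: about 90 − 30 = 60 days, not firm.

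**5. Women concerned.** The documents do not give the number of women of childbearing potential. As an assumption, take the feasibility cohort described in section 3 (15 of 46 female, age 60 ± 10), treat age as normal and the same in both sexes, and use age as a proxy for childbearing potential.
- Women among 500: 500 × 15/46 = 163.
- Under 45: 163 × 0.067 ≈ 11. Under 50: 163 × 0.159 ≈ 26. Under 55: 163 × 0.309 ≈ 50.

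**6. Conceptions in the 83 days.** Woman-years = number of women × 83/365. Conceptions = woman-years × annual failure rate, assumed to be 1% to 10%.

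| Women assumed | Woman-years | Conceptions at 1% | Conceptions at 10% |
|---|---|---|---|
| 11 (under 45) | 2.48 | 0.02 | 0.25 |
| 26 (under 50) | 5.88 | 0.06 | 0.59 |
| 50 (under 55) | 11.44 | 0.11 | 1.14 |

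These are upper bounds under the stated failure rates: every woman is taken to rely on a test exactly 90 days old, and the 5.2 confirmation is taken to catch none.

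**7. A milder case.** If a quarter of the 26 women rely on a carried-over test that is 45 days old on average, woman-years = 26 × 0.25 × (45 − 7)/365 = 0.68. That gives about 0.01 to 0.07 conceptions in the whole study.

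**The case against.** The strongest reply is that this is a post-market study of patients already planned for renal denervation in routine care. The procedure follows the Instructions for Use, which the documents do not reproduce, and a pregnancy check may be required there or by local practice. Table 1 lists data to be collected, so an empty cell does not show that no check is made. Three safeguards already apply: the exclusion of pregnancy and of inadequate contraception, baseline testing after enrolment as the default, and the confirmation of criteria before ablation. The carry-over is permissive and covers only tests already done. Harm needs several unlikely steps in a row.

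Most of this stands, and it is why the point is minor. It does not change what the stated rule accepts: a site can confirm eligibility from a 90-day-old negative result and still comply. Contraception lowers the chance of pregnancy but does not detect failure. If the Instructions for Use already require a recent test, saying so in the protocol does no harm.

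Two comparisons also need care. The ambulatory window runs from the baseline visit and the 90 days from the procedure, so the ambulatory limit is tighter at the procedure only if the 30-day interval is kept. The repeat office reading in 5.1.3 is triggered by a known event, a medication change; it is not a maximum-age rule. The point does not depend on either comparison.

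**Conclusion.** The concern holds as a small safety improvement to consider. The plan accepts a pregnancy result up to 90 days old as its only scheduled test and specifies none close to the procedure.

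That conclusion rests on the text alone. The size rests on assumptions: the sex and age mix of a 46-patient feasibility cohort, age as a proxy for childbearing potential, and a 1 to 10% annual contraceptive failure rate. On these, the expected number of conceptions in the avoidable period is below one in all but the most extreme combination, and about 0.01 to 0.07 in the milder case. The reason to act is that the exposure is avoidable at little cost. Whether the Instructions for Use already close the gap cannot be seen from the documents.

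**What to change.** In section 5.1 and a Table 1 footnote, exempt the pregnancy test from the 90-day carry-over. For women of childbearing potential, require a negative urine or blood test within a short window counted back from the procedure; 7 days is an example, and the sponsor should set the figure. In 5.2, state that this result is used when the exclusion criteria are confirmed.

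The 90-day rule is already counted from the procedure, so this only sets a smaller number for one test. A window tied to enrolment would not be enough, because the interval from enrolment to procedure has no firm limit.

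The cost is one clause, one footnote and one cross-reference, plus an occasional repeat test in perhaps 11 to 50 women under the assumptions above. A 7-day test can still miss a very early conception. Sample size and primary analysis do not change.

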4.5 Inclusion and Exclusion Criteria / Point of Enrollment

A patient, who meets all of the inclusion criteria, and none of the exclusion criteria, is eligible to participate in this investigation. A patient becomes a subject once he/she has been fully informed about the investigation, has agreed to participate and signed & dated the PIC form (Refer to section 6.6 for the Informed Consent Process).

Once enrolled, a subject is expected to comply with the scheduled visits and required activities according to the CIP. The subject should undergo the renal denervation procedure within 30 days of enrollment.

All subjects enrolled in the study (including those withdrawn from the study or lost to follow-up) shall be accounted for and documented in the Patient Identification Log, assigning an identification code linked to their names, alternative identification or contact information. Because subject privacy and confidentiality of data must be maintained throughout the clinical investigation, this log will only remain on site. This log shall be kept up to date throughout the clinical investigation by the Principal Investigator or his/her authorized designee.

Inclusion Criteria

- Subject is planned to undergo a renal denervation procedure for the treatment of hypertension
- Subject is ≥18 years of age at time of consent
- Subject must be able and willing to provide written informed consent
- Subject must be able and willing to comply with the required follow-up schedule
- Subject has office SBP ≥ 140 mmHg

- Subject has established hypertension (diagnosed ≥ 12 months prior to baseline) and is on a guideline based drug regimen at a stable (≥ 14 days) and a fully tolerated dose consisting of ≥ 3 anti-hypertensive medications (including 1 diuretic)

Exclusion Criteria

- Subject has known significant renovascular abnormalities such as renal artery stenosis $>30\%$
- Subject has undergone prior renal angioplasty, renal denervation, indwelling renal stents, and/or abdominal aortic stent grafts
- Subject has a history of hemodynamically significant valvular heart disease
- Subject has blood clotting abnormalities
- Subject has a life expectancy less than 12 months, as determined by the Study Investigator
- Subject is participating in another clinical study which has the potential to impact his/her hypertension management (pharmaceutical / device / homeopathic)
- Subject is pregnant, nursing, or of childbearing potential and is not using adequate contraceptive methods

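### Section 5.1 can be read to let the record office SBP that met the 140 mmHg entry limit serve as the primary-endpoint baseline, and Section 8.4.1 does not say which set is the baseline

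*Combined protocol and SAP*

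**What the plan says.** The primary result is the mean change in office SBP from baseline to 6 months in one treated group. These passages bear on the baseline value:

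- **Section 4.5** sets the entry limit: "Subject has office SBP ≥ 140 mmHg". It gives no timing and asks for no separate confirmatory reading.
- **Section 5.1** has sites "evaluate potential candidates by reviewing the patient medical records against the inclusion and exclusion criteria" before enrolment. Baseline data are "collected at the baseline visit either from hospital records or through patient interaction documented in the hospital records".
- **Section 5.1** then states: "All baseline activities are performed after the patient is enrolled in the investigation". The next sentences make allowances. Standard-of-care ambulatory recordings may be up to 2 weeks old, and other tests and required assessments "performed as standard of care before the baseline visit can be used if done within 90 days prior to procedure".
- **Table 1 (Section 5)** repeats the shorter limit for ambulatory pressure only: "Ambulatory Blood Pressure Recordings of the last 2 weeks can be used". Office blood pressure is a required baseline item with no footnote.
- **Section 5.1.3**: "Office Blood Pressure measurements will be recorded as the average Blood Pressure of three measurements". If drugs change afterwards, "an additional set of office Blood Pressure measurements is required to determine eligibility". It does not say that the new set replaces the old one as the analysis baseline.
- **Section 8.4.1** subtracts from baseline and does not say which set that is.

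The 6-month value is not in question, because Section 5.4.2 has it measured at the follow-up visit.

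**The concern.** A reading that admits a subject because it is at or above a limit is, on average, above that subject's usual level. If the same reading is the baseline, part of the later fall occurs without any treatment effect. There is no control group, and no planned analysis separates this part from the reported reduction. The 90-day sentence appears to permit such reuse, and the primary measure then has a looser age limit than ambulatory pressure, which is collected only when done in routine care.

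The missing definition matters on its own. Where a subject has both a record set and a set taken at the visit, two analysts could choose differently and both comply with Section 8.4.1.

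**Working it through.** **1. The plan's own figure.** Section 8.2 gives SD 24.7 mmHg and 425 evaluable subjects. Half-width = 1.96 × 24.7 / √425 = 2.35 mmHg, as stated. The sample size is not in dispute, and 2.35 serves here only as a yardstick.

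**2. Inputs the documents do not give.** They state neither the within-person SD of office SBP, nor the share of subjects with a record baseline, nor the expected baseline level in this study. The only level given is the pilot's 176±16 (Section 3). I assume a within-person SD (sw) of 8 to 12 mmHg; a normal pool of candidate readings with mean μ and SD st of 20 mmHg (16 to 20 at the pilot's level); a constant true level; and a record baseline in every subject.

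**3. Regression to the mean when the qualifying reading is the baseline.** With z = (140 − μ)/st,

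RTM = (sw²/st) × φ(z) / (1 − Φ(z)).

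| Pool mean μ | st | z | φ(z)/(1−Φ(z)) | sw | RTM, mmHg |
|---|---|---|---|---|---|
| 145 | 20 | −0.25 | 0.646 | 8 | 64/20 × 0.646 = 2.07 |
| 145 | 20 | −0.25 | 0.646 | 12 | 144/20 × 0.646 = 4.65 |
| 160 | 20 | −1.00 | 0.288 | 8 | 0.92 |
| 160 | 20 | −1.00 | 0.288 | 12 | 2.07 |
| 176 | 16 | −2.25 | 0.032 | 8 | 0.13 |
| 176 | 20 | −1.80 | 0.082 | 12 | 0.59 |

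If only half the subjects have record baselines, halve these: 1.0 to 2.3, 0.5 to 1.0, and 0.06 to 0.3 mmHg.

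**4. What a fresh baseline removes.**

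- *Fresh set not used to select subjects.* Its error averages zero, so re-measurement removes the whole amount in step 3.
- *Fresh set also screened at 140.* In this model the record and fresh readings are exchangeable. Among subjects who pass both, their mean errors are therefore equal, and swapping one for the other changes nothing. A simulation of 4 million draws agrees (record against fresh): 1.28 and 1.29 at mean 145 with sw 8; 3.28 and 3.28 at 145 with sw 12; 0.60 and 0.61 at 160 with sw 8; 1.56 and 1.56 at 160 with sw 12.

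**The case against.** **The text.** The sentence placing all baseline activities after enrolment comes immediately before the allowances. The 90-day sentence does not name office blood pressure, and Table 1 has a single baseline entry for it. Section 5.1.3 requires an average of three guideline-method readings and a repeat set after a drug change. A site could reasonably conclude that office pressure must be measured afresh. This stands as far as it goes: the documents do not clearly prescribe an old baseline. But the allowances are exceptions to the sentence before them, and nothing exempts office pressure from them, so both readings remain open.

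**Drug changes.** A reader might infer that a record reading could predate a change of regimen and so contaminate the baseline. Section 5.1.3 largely closes that route. The concern is limited to unchanged drugs, apart from the missing statement that the repeat set becomes the baseline.

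**The gain from re-measuring.** A reader might compare the total in step 3 with the amount left in subjects who pass two screens, and credit re-measurement with the difference: 0.8 to 1.4 mmHg at mean 145, 0.3 to 0.5 at 160, and 0.02 to 0.1 at 176. The comparison is between different groups of subjects. The difference comes from dropping those who fail a second screen (14.8 to 22.5% at 145, 6.5 to 9.7% at 160, 0.8 to 2.6% at 176). It is the effect of a second eligibility screen, not of a new baseline.

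**Whether the fresh set is screened.** Section 8.3 treats enrolled subjects who fail the criteria before the procedure as screen failures, and Section 5.2 has the criteria confirmed before ablation. Both lean towards screening, in which case re-measurement alone brings no numerical gain among retained subjects. This also stands, and the fix must address it.

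**Purpose.** The primary objective is descriptive, Sections 8.2 and 8.4.1 set no success threshold, and use of routine-care data is deliberate. That lowers the severity but does not remove the need for a defined baseline.

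**Conclusion.** The point holds as a minor one. Section 5.1 is open to a reading under which the qualifying record value is the primary baseline, and Section 8.4.1 does not settle which set is used.

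The size rests wholly on the assumptions in step 2: 2.1 to 4.7 mmHg at pool mean 145, 0.9 to 2.1 at 160, and 0.1 to 0.6 at 176. A reader might infer that the bias is known to exceed the planned half-width. The documents do not support that. Of the cases worked, only the larger SD at mean 145 exceeds 2.35 mmHg, and at the only level the documents give the effect is small. It matters if many enrolled pressures lie near 140 and record baselines are common.

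Nor can a fresh baseline be said to remove the regression to the mean in all cases. It does so only where the fresh set plays no part in selection.

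**What to change.** - **Section 5.1:** reconcile the two sentences by excluding office blood pressure from the 90-day allowance.
- **Section 8.4.1:** define the analysis baseline as the average of three office readings taken at the baseline visit, after enrolment and before the procedure, or the repeat set where Section 5.1.3 requires one. Keep it separate from the record reading that established eligibility.
- **Sections 5.2 and 8.3:** reconcile whether the baseline set also determines eligibility. If it does, state that regression to the mean remains in the reported reduction.
- **Subjects already enrolled:** tabulate the source of each baseline (record or visit) and its age in days before the procedure, and show the mean reduction by source.

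This is a cheap improvement: three readings at an existing visit, some wording changes and one descriptive table. Sites could no longer reuse old office readings for the baseline, and the reported reduction may be smaller. The sample size is unaffected.
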